1.5 Rationale

In light of our increasing experience with MRgRT and adaptive planning and advances in MR-only planning, we propose here to evaluate the feasibility and safety of same-session MR-only simulation and treatment with SMART for spinal metastases. Although spine SBRT is a standard-of-care treatment modality, this expedited same-session MR-only simulation and treatment with SMART workflow is novel. Previously, delivery of spine SBRT has typically required several days from time of consultation to simulation and then 1-2 weeks from simulation to the initiation of treatment. On this proposed study, patients will not undergo CT simulation and will instead have same-session MR-only simulation

and treatment planning, on-table, using SMART. In this manner, patients would initiate treatment within just several days from the consult. Feasibility of the workflow will be defined as successful delivery of the first fraction of same-session MRI-only simulation and treatment with SMART on the first on-table attempt for at least 70% of patients. Patients will be treated in either a two or five fraction course over 1-2 weeks. Although our long-term goal will be to achieve a significantly shortened time from consult to treatment as compared to traditional SBRT using simulation, the present study will be driven by short-term goals of workflow feasibility and safety.

2 OBJECTIVES AND ENDPOINTS

Objectives	Endpoints	Justification for Endpoints
Primary		
Demonstrate that same-session MRI-only simulation and treatment with stereotactic MRI-guided radiotherapy (SMART) for spinal oligometastases is feasible by confirming that the first fraction of same-session MRI-only simulation and treatment with SMART can be delivered on the first on-table attempt for at least 70% of patients.	Delivery of the first fraction of same-session MRI-only simulation and treatment with SMART within the first on-table attempt for at least 70% of patients.	Clinically relevant
Exploratory		
1. Determine the average time (days) from patient consult appointment to successful delivery of the first treatment fraction.	Average time (days) from patient consult appointment to successful delivery of the first treatment fraction.	Clinically relevant
2. Determine the local, in-field tumor response and control rates at three months.	Local control rate Local in-field tumor response	Clinically relevant
3. Demonstrate that same-session MR-only simulation and treatment with SMART for treatment of spinal metastases will lead to comparable toxicities compared with historically reported rates using standard, CT-based SBRT assessed prospectively at three months post-treatment and retrospectively for later time-points.	CTCAE version 5, treatment related Grade 3 or higher toxicities	Clinically relevant
4. Determine the projected dosimetric differences between the study method of MRI-only planning using standard	Dosimetric differences between MRI-only planning using standard bulk density	Generation of preliminary data for

bulk density override dose calculations (which will be clinically used for all patients) and an exploratory alternative method of a novel voxel-by-voxel MRI-based dose calculation using an institutionally developed machine learning algorithm (which will be simulated for comparison but not used in clinical treatment planning).
	
override dose calculations and voxel-by-voxel MRI-based dose calculation using MLA
	
future radiation planning techniques.

5. Determine the on-table time required for same-session MR-only simulation and treatment with plan generation for the initial treatment fraction and for subsequent treatment fractions.
	
On-table time required for initial treatment fraction and subsequent treatment fractions
	
Clinically relevant

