5.3 Definitions of Evaluability

Endpoint	In order to be evaluable for this endpoint, a patient must have...
Primary: Feasibility	Received simulation
Exploratory: Time from consult to delivery of first fraction	Had a consult and received at least 1 fraction of RT
Exploratory: Local, in-field tumor response rates at 3 mos	Received any study treatment and undergone volumetric imaging at 3 mos
Exploratory: Local, in-field tumor control rate at 3 mos	
Exploratory: Grade 3 or higher toxicity	Received any study treatment
Exploratory: Dosimetric differences between MRI-only planning using standard bulk density override dose calculations and voxel-by-voxel MRI-based dose calculation using MLA	Received MRI and dose calculated using bulk density vs voxel-by-voxel
Exploratory: On-table time required for initial treatment fraction and subsequent treatment fractions	Received at least 1 fraction of RT

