7 REGULATORY AND REPORTING REQUIREMENTS

The entities providing oversight of safety and compliance with the protocol require reporting as outlined below. Please refer to Appendix B for definitions and Appendix C for a grid of reporting timelines.

Adverse events will be tracked from start of treatment through the 3-month post-treatment follow-up visit. All adverse events must be recorded on the toxicity tracking case report form (CRF) with the exception of:

- Baseline adverse events, which shall be recorded on the medical history CRF
- Grade 1-2 AEs regardless of relatedness
- Grade 3-4 AEs that predate SBRT
- Grade 3-4 AEs that are not at least probably attributable to treatment

Refer to the data submission schedule in Section 9 for instructions on the collection of AEs in the EDC.

Reporting requirements for Washington University study team may be found in Section 7.1.

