12.2 Sample Size Calculation

As a pilot study, the sample size is determined based on clinical considerations rather than statistical power. For our primary objective, our goal will be to report the description of same-session MR-only simulation and treatment with SMART treatment workflows, adaptation, and the time to delivery of first treatment fraction. Goal accrual will be 10 evaluable patients. For the secondary objectives, sample size is also based on clinical considerations rather than statistical power.

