12.3 Statistical Analysis Plan

Regarding toxicity, we will report descriptive statistics for acute toxicity at a three-month time point. Toxicity rates are anticipated to be identical to those of other linear accelerator based SBRT treatments. Because spine SBRT is a standard-of-care treatment that is not in and of itself investigational, further prospective toxicity assessments are not indicated. Given that no prior data exists for same-session MR-only simulation and treatment with SMART for spinal metastases, we will report descriptive statistics. As a pilot study we will establish these baseline parameters.

The primary objective is to demonstrate that same-session MRI-only simulation and treatment with stereotactic MRI-guided radiotherapy (SMART) for spinal oligometastases is feasible by confirming that the first fraction of same-session MRI-only simulation and treatment with SMART can be delivered on the first on-table attempt for at least 70% of patients.

Our principle objectives in this trial will be to determine the feasibility and safety of for same-session MR-only simulation and treatment with stereotactic MR-guided online-adaptive radiotherapy (SMART) for treatment of spinal oligometastatic disease. If we can successfully deliver the first treatment fraction at time of the first on-table treatment attempt in 70% of patients, while maintaining the safety and efficacy profile of standard spine SBRT, we will consider this study as having provided sufficient pilot data to support more widespread study of same-session SMART paradigm. The long-term goals will be to improve patient outcomes and care by reducing time to treatment, through an expedited radiotherapy delivery workflow for spinal SBRT.

All exploratory aims will be analyzed at the end of the study.

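### Objective 3 and the Section 12.3 success statement claim a toxicity comparison that about 10 patients, with no historical rate or margin, cannot support; the adverse event recording rule adds a further limit

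*Combined protocol and SAP*

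**What the plan says.** Section 2 lists five exploratory objectives. Four are to determine something. The third is to demonstrate that the workflow "will lead to comparable toxicities compared with historically reported rates using standard, CT-based SBRT", assessed prospectively at three months and retrospectively afterwards. Appendix E repeats it. Its endpoint is "CTCAE version 5, treatment related Grade 3 or higher toxicities".

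On size, Section 12.2 states "Goal accrual will be 10 evaluable patients" and explains that "the sample size is determined based on clinical considerations rather than statistical power". Section 5.3 defines the toxicity set as patients who "Received any study treatment"; feasibility evaluability requires only simulation.

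On analysis, Section 12.3 says "we will report descriptive statistics for acute toxicity at a three-month time point" and adds: "Toxicity rates are anticipated to be identical to those of other linear accelerator based SBRT treatments". It names feasibility and safety together as the trial's main aims. The pilot is to be called sufficient if 70% of patients receive the first fraction at the first attempt while the safety and efficacy profile of standard spine SBRT is preserved.

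On recording, Section 7 lists what need not go on the toxicity form, including "Grade 3-4 AEs that are not at least probably attributable to treatment". Section 9.1 carries the exceptions into the Toxicity Form. Section 7.2 says that events not needing expedited reporting must nonetheless be entered in the EDC.

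**The concern.** A demonstration of comparability needs three things: a reference rate, a margin within which a difference counts as comparable, and a rule that turns the data into a conclusion. The documents supply none of them. Even if they did, ten patients carry very little information about an uncommon event.

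The success statement raises the stakes. Safety is part of the condition for moving to wider study of a workflow that Section 1.5 itself calls novel, so few or no events could be read as meeting a condition that the data cannot test.

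Recording is a second, separate weakness. The endpoint says only treatment related, with no link to the at-least-probable threshold that governs what enters the form. If possibly related grade 3-4 events are left off, the rate cannot later be recomputed from that form under a broader definition.

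**Working it through.** The plan has no figure to reproduce: 10 is not derived from any statistical input. The check is therefore what 10 patients can show.

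**Inputs.** n = 10 (Section 12.2), taken as the toxicity denominator. Historical rate, margin and significance level: none given, so the values below are assumptions.

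**1. Precision (exact Clopper-Pearson, two-sided 95%).**
- For 0/10 the upper limit is 1 − 0.025^(1/10) = 30.8%.
- For 1/10 the lower limit is 1 − 0.975^(1/10) = 0.3%. The upper limit solves (1−p)^10 + 10p(1−p)^9 = 0.025, which gives 44.5%.
- For 2/10 the interval is 2.5 to 55.6%.
- If one simulated patient were never treated, the denominator would be 9, and 0/9 gives 1 − 0.025^(1/9) = 33.6%.

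**2. Chance of a clean or nearly clean result.** P(0 events) = (1−p)^10, which is 82%, 60%, 35% and 11% at assumed true rates of 2%, 5%, 10% and 20%. At 20%, P(0) = 0.8^10 = 0.107 and P(1) = 10 × 0.2 × 0.8^9 = 0.268, so P(at most 1) = 0.376.

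**3. Could the best possible result show comparability?** Take a one-sided test at 0.05 of the hypothesis that the true rate is at least the historical rate h plus a margin m. With 0/10 events the exact p-value is (1 − h − m)^10:

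| Assumed h | m = 5 points | 10 points | 15 points | 20 points |
|---|---|---|---|---|
| 2% | 0.484 | 0.279 | 0.155 | 0.083 |
| 5% | 0.349 | 0.197 | 0.107 | 0.056 |
| 10% | 0.197 | 0.107 | 0.056 | 0.028 |

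In 11 of the 12 combinations even zero events cannot reject. In the twelfth (h = 10%, m = 20 points) only zero events reject, so power at a true rate of 10% is 0.9^10 = 35%.

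**4. Does the stopping rule fill the gap?** Section 12.1 suspends the trial at more than 2 of the first 5 or more than 4 of the first 10. The chance that either limit is crossed is P(X₅ ≥ 3) + Σ P(X₅ = a) · P(X′₅ ≥ 5 − a) over a = 0, 1, 2, where X₅ and X′₅ are the event counts in the first and second five patients. This gives 0.9%, 7%, 22% and 45% at true rates of 10%, 20%, 30% and 40%. Not stopping is therefore weak evidence about the rate.

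**5. Recording.** One possibly related grade 3-4 event left off the form would turn 1/10 into 0/10, moving the interval from 0.3–44.5% to 0–30.8%. Grade 5 events are not in the exception list, so the gap concerns grades 3-4 only.

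**The case against.** The strongest reply is that the objective is exploratory, the sample size is openly not based on power, and Section 12.3 promises only description and baseline parameters. No test hangs on comparability. This stands: a reader might infer a failed power calculation or a need for more patients, and the documents support neither. What it does not answer is the mismatch between the descriptive analysis and the two claims, one of them in the success statement.

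Other stronger readings also fail.
- **Zero events will be declared comparable.** No text says so. It is a risk created by the wording, not a stated rule.
- **There is no attribution definition.** Appendix C refers attribution to the OHRP definitions, and Sections 7 and 12.1 use a similar working threshold. What is missing is the link from the endpoint to that threshold.
- **Possibly related events are recorded nowhere.** Section 7.2 requires EDC entry of events outside expedited reporting, and Appendix D sends adverse events of that kind to the toxicity table of the monitoring report. The sections conflict, so capture is unclear rather than absent.
- **The rate is biased downward.** This holds only against a series that counted possibly related events. If the series used a probable-or-definite threshold, this source of bias disappears.

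The expectation of identical rates in Section 12.3 is just that, an expectation and not an analysis claim.

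**Conclusion.** The point holds as a mismatch between what is claimed and what the design can deliver. About 10 treated patients, analysed descriptively with no reference rate, margin or rule, cannot demonstrate comparable toxicity or a preserved safety profile. The best possible outcome, no events, still leaves rates up to 30.8% inside the 95% interval. The intervals rest only on a denominator of 10. The 20% rate and the grid of historical rates and margins are illustrations, because the documents give none.

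The recording rule is a secondary, conditional weakness. It limits recomputation from the Toxicity Form, and its effect on any comparison depends on counting rules that the documents do not state. The feasibility count in the primary endpoint is unaffected. The change should be made, and the recording part needs to come before data collection ends, because unrecorded events may not be recoverable.

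**What to change.** 1. Reword Objective 3 and its Appendix E copy to estimate the rate of treatment-related grade 3 or higher toxicity at three months with an exact 95% interval. Keep the retrospective later time-points, labelled descriptive only.
2. In Section 12.3, replace the condition on preserving the safety profile with reporting of that rate and interval, and make no claim of comparability.
3. Reconcile Sections 7 and 9.1 with Section 7.2 by recording grade 3-4 events judged possibly related, each with its attribution. State which attribution levels count as treatment related for the endpoint, and report the rate with and without the possibly related events.

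The cost is a few sentences, a few more adverse event entries in about 10 patients, and a less favourable claim. Sample size, treatment and stopping rule stay as they are.

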3 STUDY POPULATION

3.1 Inclusion Criteria

1. At least one disease site deemed to be suitable for treatment with spine SBRT as per radiation oncology evaluation.
2. Karnofsky Performance Status (KPS) ≥ 60 .
3. Deemed medically fit for SBRT by treating physician
4. Diagnostic CT with images through the projected treatment area within six months prior to enrollment.
5. At least 18 years of age.
6. Ability to understand and willingness to sign an IRB approved written informed consent document.

3.2 Exclusion Criteria

1. Past history of radiotherapy within the projected treatment field to be treated by MRI-guided SBRT
2. Medical contraindication to undergoing MR imaging.
3. Spine metastasis resulting in symptomatic spinal cord compression.
4. Any other condition that, in the opinion of the treating radiation oncologist, renders the patient unfit for SBRT.
5. Pregnant and/or breastfeeding. Women of childbearing potential must have a negative pregnancy test within 14 days of study entry.

3.3 Inclusion of Women and Minorities

Both men and women and members of all races and ethnic groups are eligible for this trial.

4 REGISTRATION PROCEDURES

Patients must not start any protocol intervention prior to registration through the Siteman Cancer Center.

The following steps must be taken before registering patients to this study:

1. Confirmation of patient eligibility
2. Registration of patient in the Siteman Cancer Center database
3. Assignment of unique patient number (UPN)

4.1 Confirmation of Patient Eligibility

Confirm patient eligibility by collecting the information listed below:

1. Registering MD's name
2. Patient's race, sex, and DOB
3. Three letters (or two letters and a dash) for the patient's initials
4. Copy of signed consent form
5. Completed eligibility checklist, signed and dated by a member of the study team
6. Copy of appropriate source documentation confirming patient eligibility

4.2 Patient Registration in the Siteman Cancer Center OnCore Database

All patients must be registered through the Siteman Cancer Center OnCore database.

4.3 Assignment of UPN

Each patient will be identified with a unique patient number (UPN) for this study. All data will be recorded with this identification number on the appropriate CRFs.

4.4 Screen Failures

Screen failures are defined as participants who consent to participate in the clinical trial but are not subsequently entered in the study. A minimal set of screen failure information is required to ensure transparent reporting of screen failure participants, to meet the Consolidated Standards of Reporting Trials (CONSORT) publishing requirements and to respond to queries from regulatory authorities. Minimal information includes demography, screen failure details, eligibility criteria, and any serious adverse event (if applicable).

4.5 Strategies for Recruitment and Retention

Patients will be accrued on basis of presentation to the radiation oncology clinic with spinal metastasis amenable to SBRT. Potential participants will be identified in the inpatient and outpatient radiation oncology clinic setting, as well as from the multidisciplinary spine tumor board. Patients will be approached regarding participation at or around the time of

their radiation oncology consultation visit. Patients will be treated at a single facility, at the Siteman Cancer Center's Center for Advanced Medicine clinic, as the technology required for this study is confined to this center. We anticipate an accrual rate of approximately 15 patients per year, or an estimated study accrual period of 8-12 months. There will be no compensation or incentives offered for study participation.

5 TREATMENT PLAN

5.1 Study Intervention Description and Administration

Radiotherapy will consist of stereotactic body therapy to the spine, to be given over two or five fractions, delivered once daily or once every other day for a period of one to two weeks, for a total of two or five treatments.

5.1.1 Dose, Fractionation

Radiotherapy will consist of stereotactic body therapy, to be given over either a two or five fraction course, delivered once daily or once every other day for a period of one to two weeks, for a total of two or five treatments (depending on whether a 2 or 5 fraction course is selected). Patients will be planned for an initial prescription dose at the discretion of the treating physician, delivered in two or five total fractions to the PTV, with dose adaptation based on safety constraints that are already approved of to prevent OAR injury. Suggested dose prescriptions are 24 Gy in 2 fractions or 35 Gy in 5 fractions.

[figure not shown]
5.1.2 Patient Positioning

All patients will undergo volumetric MR imaging on treatment days in positioning appropriate for the specific treatment site.

5.1.3 Clinical Target Volume (CTV) and Planning Target Volume (PTV) Definitions

The treatment target will be defined based on the clinical target volume (CTV) only, based on International Spine Radiosurgery Consortium (ISRC) consensus guidelines. The PTV will be generated at the discretion of the treating physician but will generally range between 3 mm and 7 mm.

Vertebral bodies are divided into 6 sectors as illustrated below from the ISRC consensus guidelines:

CTV definitions are listed below and use the previously defined sectors to delineate volumes:

Tumor involvement	ISRC bony CTV recommendation	CTV description
Any portion of the vertebral body	1	Include the entire vertebral body
Lateralized within the vertebral body	1, 2	Include the entire vertebral body and the ipsilateral pedicle/transverse process
Diffusely involves the vertebral body	1, 2, 6	Include the entire vertebral body and the bilateral pedicles/transverse processes
Tumor involves vertebral body and unilateral pedicle	1, 2, 3	Include entire vertebral body, pedicle, ipsilateral transverse process, and ipsilateral lamina
Tumor involves vertebral body and bilateral pedicles/transverse processes	2, 3, 4	Include entire vertebral body, bilateral pedicles/transverse processes, and bilateral laminae
Tumor involves unilateral pedicle	2, 3 ± 1	Include pedicle, ipsilateral transverse process, and ipsilateral lamina, ± vertebral body

Tumor involves unilateral lamina	2, 3, 4	Include lamina, ipsilateral pedicle/transverse process, and spinous process
Tumor involves spinous process	3, 4, 5	Include entire spinous process and bilateral laminae

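### In the CTV table, the row for tumor in the vertebral body and both pedicles carries sector codes (2, 3, 4) that contradict its own description; read by the codes, the involved vertebral body falls outside the target.

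*Combined protocol and SAP*

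**What the plan says.** Protocol section 5.1.3 bases the target on the CTV, following the International Spine Radiosurgery Consortium consensus guideline. It introduces a numbering: "Vertebral bodies are divided into 6 sectors as illustrated below from the ISRC consensus guidelines". It then says how the numbers are used: "CTV definitions are listed below and use the previously defined sectors to delineate volumes".

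The table that follows has eight rows. Each row gives a tumor pattern, a set of sector codes and a description in words. The row at issue reads: "Tumor involves vertebral body and bilateral pedicles/transverse processes 2, 3, 4 Include entire vertebral body, bilateral pedicles/transverse processes, and bilateral laminae".

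The protocol does not say which column prevails if the codes and the description differ.

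**The concern.** The two columns of this row describe different volumes, and both cannot be followed. Someone contouring from the description would include the vertebral body, both pedicles/transverse processes and both laminae. Someone contouring from the codes would include one pedicle/transverse process, one lamina and the spinous process, and would leave out a vertebral body and an opposite pedicle that the row itself says contain tumor.

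The PTV is an expansion of the CTV, so an error in the CTV carries through. The coverage goal in section 5.1.4 is a percentage of the volume drawn, so a plan can meet it on the wrong volume. Under the two readings, target coverage, organ-at-risk dose and three-month in-field response and control would refer to different fields in patients with the same disease pattern.

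**Working it through.** No sample-size or error-rate formula is involved; this is a consistency check on the table in section 5.1.3.

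**Step 1: a test that needs no key.** The codes 2, 3, 4 appear in two rows. In the row at issue the description includes the vertebral body. In the unilateral lamina row it does not: it lists the lamina, the pedicle/transverse process on that side and the spinous process. If the codes keep one meaning throughout the table, one set of codes cannot stand for both volumes.

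**Step 2: recover the key from the other seven rows.** In the table below, near means the involved side, far means the opposite side, and pedicle stands for pedicle/transverse process.

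| Tumor pattern | Codes | Structures described | What it fixes |
|---|---|---|---|
| Any part of the body | 1 | body | 1 = body |
| Lateralized in the body | 1, 2 | body, near pedicle | 2 = near pedicle |
| Diffuse in the body | 1, 2, 6 | body, both pedicles | 6 = far pedicle |
| Body and one pedicle | 1, 2, 3 | body, near pedicle, near lamina | 3 = near lamina |
| One pedicle | 2, 3 ± 1 | near pedicle, near lamina, ± body | agrees with the rows above |
| One lamina | 2, 3, 4 | near lamina, near pedicle, spinous process | 4 = spinous process |
| Spinous process | 3, 4, 5 | spinous process, both laminae | 5 = far lamina |

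The first, third and last of these rows read in full: "Any portion of the vertebral body 1 Include the entire vertebral body"; "Diffusely involves the vertebral body 1, 2, 6 Include the entire vertebral body and the bilateral pedicles/transverse processes"; "Tumor involves spinous process 3, 4, 5 Include entire spinous process and bilateral laminae".

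Six codes can be assigned one-to-one to six structures in 6! = 720 ways. Testing all 720 against these seven rows (the one-pedicle row both with and without sector 1) leaves exactly one, the key shown. The sector illustration, which is not reproduced in the text available here, is therefore not needed.

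**Step 3: apply the key to the row at issue.**

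- Description: body, both pedicles, both laminae = {1, 2, 3, 5, 6}.
- Printed codes: {2, 3, 4} = near pedicle, near lamina, spinous process.
- In both: {2, 3}.
- Described but not coded: {1, 5, 6} = body, far lamina, far pedicle, which is 3 of the 5 described sectors.
- Coded but not described: {4} = spinous process.

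**Step 4: could another numbering rescue the row?** No. Three codes cannot name five distinct structures, and none of the 720 assignments makes this row's codes match its description.

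**The case against.** The mismatch itself is hard to dispute; the case on the other side concerns its consequence.

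- **The row warns the reader.** The vertebral body is named both in the tumor pattern and in the description, on either side of the wrong codes. To leave it out, a planner would have to use the codes alone, and nothing in the protocol shows that anyone does.
- **The guideline, not the codes, is the stated basis.** Section 5.1.3 refers to the consensus guideline, and Appendix A labels its planning targets in words.
- **There are earlier and later looks.** Section 5.1.4 has a pre-plan made from the diagnostic MRI before the first treatment day. Section 5.1.7 includes contours among the plan-integrity checks and requires a physics review before delivery.
- **The trial's conclusion is little affected.** The primary endpoint is whether the first fraction is delivered at the first on-table attempt. In-field response and control are exploratory, in about 10 patients, and prescription dose and PTV margin already vary by physician choice.

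Much of this stands as an argument about likelihood. An experienced physician would probably notice that the diseased vertebral body is missing, and this is more likely a transcription slip than a deliberate choice.

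It does not remove the problem. The section says the definitions "use the previously defined sectors to delineate volumes", so the code column is operative. No rule says that the words prevail. The protocol describes no check of the drawn CTV against this table, and the pre-plan gives no independent check if it is drawn from the same table. Final delineation is also done with the patient on the table, where time is short.

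One caution on the count: the agreement of the other seven rows is partly built in, because six of them were used to fix the six codes. The one-pedicle row is the only separate confirmation. The contradiction does not depend on that count, since steps 1 and 4 establish it without the key.

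**Conclusion.** The concern holds. As written, the protocol gives two incompatible target volumes for one disease pattern, and by its own numbering one of them leaves out bone that the row says contains tumor. One of eight rows is affected; its codes miss three of five described sectors and add one. This rests on two assumptions: that each code means the same thing in every row, and that pedicle and transverse process form one sector, as the table treats them.

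The harm is conditional on someone planning from the codes. The documents do not say how many patients fall under this row. The primary endpoint and the sample size are unaffected. For the exploratory response and control rates, one patient with a differently defined field carries 1/10 = 10 percentage points if all 10 planned evaluable patients have three-month imaging, and more if fewer do.

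The correction is needed because the table directs where high-dose treatment is placed beside the spinal cord, and it should not depend on the reader overriding it. This review takes no view on which of the two volumes is clinically right.

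**What to change.** Reconcile the codes and the description in this row against the consensus guideline that section 5.1.3 cites, so that both define the same volume. Add a sentence saying which column governs contouring if the two differ, and issue that statement at once as an interim instruction. Review any patient already planned under this row, and record which reading was used so that the dosimetry and three-month in-field results can be interpreted.

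The cost is one table row and one sentence in an amendment, plus a record check for any affected patients. It needs no added procedures, visits or participants.
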